Alongside with HAM-A scale we will also use serum cortisol levels as a biomarker for anxiety disorders in our population. Cortisol levels will be analyzed in a similar way to HAM-D and HAM-A scores using mixed analysis of covariance (Mixed ANCOVA) with covariates being: Baseline Cortisol serum levels (V0), Childhood trauma questionnaire score at V0, Age, Sex (Male=0, Female=1), Smoking status (0=Non-smoker, 1=Smoker), Alcohol consumption (0=No, 1=Yes), Metabolic syndrome (0=No, Yes). Additionally, correlation between HAM-A score and cortisol levels will be tested.

Since stress, trauma and socio-economic status can all be a part of depressive disorder pathogenesis, we will explore these environmental factors in order to determine their role in the clinical pictures of our participants. Outcome measures used will be:

1. Perceived stress score measured at baseline, visit 1 and visit 2,
2. Childhood trauma score measured at baseline,
3. Employment status (1=Unemployed, 2=Employed; monthly incomes <40 000 RSD, 3=Employed; monthly incomes 40 000-80 000 RSD, 4=Employed; monthly incomes >80 000RSD).
4. Marital status (1=Unmarried, 2=Married, 3=Divorced, 4=Widowed)
5. Education level (1=Primary education (8 years), 2= High school diploma (8+3 or 8+4 years), 3= Associate's degree (8+4+2 or 8+4+3 years) 4= Bachelor's degree (8+4+4 years or higher)

We will separately test for the correlation between these variables and HAM-D score, HAM-A score and CGI-S score.

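### Separate pairwise correlations cannot separate the roles of stress, trauma and socio-economic factors, and a correlation with the marital status code has no clear meaning

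*Combined protocol and SAP*

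**What the plan says.** The closing part of the Statistical Analysis Plan, under Other outcome measures/observations, gives the aim: "we will explore these environmental factors in order to determine their role in the clinical pictures of our participants". Five variables follow:

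- "Perceived stress score measured at baseline, visit 1 and visit 2"
- "Childhood trauma score measured at baseline"
- a four-level code that combines employment with income band, beginning "Employment status (1=Unemployed, 2=Employed; monthly incomes <40 000 RSD"
- "Marital status (1=Unmarried, 2=Married, 3=Divorced, 4=Widowed"
- a four-level education code, beginning "Education level (1=Primary education (8 years), 2= High school diploma"

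The analysis is one sentence: "We will separately test for the correlation between these variables and HAM-D score, HAM-A score and CGI-S score". It names no visit, type of correlation coefficient, alpha, adjustment set or joint model.

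Elsewhere, childhood trauma is a covariate in the HAM-D, HAM-A and cortisol models and, by reference to the HAM-D set, in the CGI models. Those models compare the dosing groups. None contains perceived stress, employment/income, marital status or education.

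**The concern.** The aim is to determine each factor's role; the method looks at one factor and one scale at a time. It is plausible that education goes with income, childhood trauma with perceived stress, and marital status with age. Where that is so, a pairwise correlation combines the factor's own association with that of whatever it travels with. A report could then name education as having a role when the association belongs to income, or marital status when it belongs to age.

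This is bias and not chance error, so a larger trial makes the false attribution more likely.

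The second problem is one of measurement level. Marital status is a set of unordered categories numbered 1 to 4, and a correlation treats those numbers as an ordered scale.

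What is at stake is how one exploratory section is interpreted. None of the four hypotheses involves these factors.

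**Working it through.** **Inputs.** The documents state no sample size, expected correlation or alpha for this analysis, so there is no planned figure to reproduce. All of the following are assumptions:

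- Factor A (say education) has no association with the outcome once factor B (say income) is known.
- B correlates b = 0.3 with the outcome.
- A and B correlate r = 0.4 to 0.5.
- Tests are two-sided at 0.05, with n = 100 or 200.

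**Step 1: the correlation that A will show.** It equals r × b:

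- 0.4 × 0.3 = 0.12
- 0.5 × 0.3 = 0.15

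**Step 2: the chance that A is significant.** By the Fisher z approximation, m = atanh(r × b) × √(n − 3), and the chance is Φ(m − 1.96) + Φ(−m − 1.96). Here atanh(0.12) = 0.1206 and atanh(0.15) = 0.1511.

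| n | r × b | m | Chance that A is significant |
|---|---|---|---|
| 100 | 0.12 | 0.1206 × √97 = 1.19 | 22% |
| 100 | 0.15 | 0.1511 × √97 = 1.49 | 32% |
| 200 | 0.12 | 0.1206 × √197 = 1.69 | 40% |
| 200 | 0.15 | 0.1511 × √197 = 2.12 | 56% |

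A factor with no association of its own should reach significance in 5% of trials.

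**Step 3: sensitivity.** Over n = 50 to 300, b = 0.3 to 0.5 and r = 0.2 to 0.6, the chance runs from 7% (n = 50, b = 0.3, r = 0.2) to nearly 100% (n = 300, b = 0.5, r = 0.6). With r = 0 it returns to 5%, so the problem exists only to the extent that the factors are related.

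**Step 4: both factors in one model.** In 5,000 simulated trials per setting (n = 50, 100, 200; b = r = 0.3, 0.4, 0.5), the adjusted coefficient of A was significant in 4.4% to 5.4%. At n = 100 and b = r = 0.4, the pairwise test rejected in 35% and the adjusted test in 4.4%. The simulation assumes that A has nothing to add once B is known. It confirms that the joint model behaves properly in that case, not that the trial's factors behave this way.

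**Step 5: marital status.** A Pearson correlation takes the steps from unmarried to married, married to divorced and divorced to widowed as equal. A rank correlation still takes the categories as ordered. Renumbering them would change either coefficient with no change in the patients. The employment item is less arbitrary, but its first step is employment and its later steps are income, so a single slope is also hard to read.

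**The case against.** **Description is a legitimate answer.** The plan says that it will explore these factors, and an association with symptom severity is a fair descriptive finding. This stands in part. The correlations can stay as unadjusted description, but they do not support a statement of "in order to determine their role in the clinical pictures of our participants" factor by factor.

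**Mutual adjustment can mislead too.** If education acts through income, or trauma through current stress, a model with all factors removes part of a real, indirect association and may report none. This stands. No single model defines every factor's role, so the fix shows more than one.

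**The size is assumed.** This stands. The documents do not show that the factors are correlated, so the claim is that a factor can be wrongly credited, not that one will be.

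Two stronger readings that a reader might infer are not supported:

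- *That this is the one unadjusted analysis of these scales.* It is not. The same part of the plan also correlates HAM-A with cortisol without adjustment. What is adjusted is the set of group comparisons on these scales.
- *That dosing group distorts the correlations at V1 and V2.* The plan names no visit for them. In the standard course everyone takes 10 mg/day until V1, and group could distort a correlation only if the environmental factors were related to group. Nothing in the documents shows that. Adjusting for the baseline score at later visits would also turn a question about severity into one about change.

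**Conclusion.** The point holds as a minor mismatch between aim and method. Separate correlations cannot tell a factor's own association from that of related factors, age or sex, and nothing elsewhere in the documents supplies the missing analysis.

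The figures of 22–32% at n = 100 and 40–56% at n = 200 rest on assumed correlations, an assumed sample size and an assumed alpha. They would be smaller with weaker relations between the factors and would vanish with none. The objection to correlating the marital status code needs no such assumption.

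No primary or secondary result depends on this section. It would also be going too far to conclude that one jointly adjusted model settles each factor's role, since some of the five may lie on the path from others to symptoms.

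**What to change.** Amend the paragraph on environmental factors as follows.

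1. Keep the pairwise correlations as unadjusted description only, and leave out the correlation with the marital status code; show the scores by category instead.
2. For HAM-D, HAM-A and CGI-S at baseline, fit a regression for each factor adjusted for age and sex, with marital status and employment/income entered as categories.
3. Beside these, show one model per scale with all five factors, age and sex, with and without perceived stress, because stress may lie on the path from trauma or income to symptoms.
4. Report coefficients with confidence intervals, label the results exploratory, and state that no single jointly adjusted coefficient is to be read as a factor's total role.

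**Cost.** The data are already collected under the plan. The work is one paragraph of SAP text and, per scale, 5 factor-specific models plus 2 joint ones: 7 × 3 = 21 short regressions.

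**Downside.** Intervals will be wider. With education as a single ordered term, the full model has 1 (stress) + 1 (trauma) + 3 (employment/income) + 3 (marital status) + 1 (education) + 1 (age) + 1 (sex) = 11 coefficients. Since no sample size is stated, the loss of precision cannot be judged now. Each coefficient's meaning will also depend on what else is in the model, which is why the versions should be shown side by side.

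If the sponsor prefers not to add models, the smaller change is to restate the aim as describing unadjusted associations and to handle marital status as categories.
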